
Primary aim. To compare total MPA (min/wk.) across the 6-mo. active intervention in adults with AD and their caregiver randomized to RGV and EUC. We expect greater MPA in the RGV compared to EUC arm.

Secondary aims: To compare the following across 18 mos. between RGV and EUC. *Adults with AD:* MPA (min/wk.), sedentary time (min/wk.), percentage meeting 150 min/wk. goal, functional fitness, activities of daily living (basic/instrumental), quality of life, residential transitions, neuropsychiatric symptoms, cognitive function. *Caregivers:* Total MPA (min/wk.), sedentary time (min/wk.), functional fitness, quality of life, caregiver burden. We expect more favorable changes for all secondary outcomes for both adults with AD and caregivers in the RGV compared with the EUC arm.

Exploratory aim. To evaluate the influence of process variables/ characteristics on MPA in adults with AD and their caregiver across 18 mos.: age, sex, BMI, attendance (exercise/support sessions), use of recorded sessions, PA self-monitoring, peer interactions during group sessions, caregiver support, level of dementia.

B. Background and Significance

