Health coach training/blinding/fidelity. Training. We currently have 3 health coaches with experience in delivering group exercise using video conferencing to adults with AD. If needed, new health coaches will be trained by Drs. [name] and [name], and will shadow an experienced health coach for a minimum of 3 mos. prior to delivering the intervention on their own. [name] will train health coaches on how to perform each exercise, the order of presentation of the exercises, and provide guidance on how to recognize and correct common mistakes in performing specific exercises. [name] will provide training regarding strategies for effective communication with adults with AD, i.e., speaking clearly and slowly, providing/repeating simple specific instructions (68), focusing on reassurance and empathy for each participant (69), and fostering interaction between participants with strategies to ensure the focus of the interactions is not on dementia (67). Blinding. The nature of this trial precludes blinding of the health coaches; however, investigators, data analysts and research assistants will be blinded to condition. Intervention fidelity. Recordings from all group exercise sessions (RGV only) and individual support sessions will be reviewed. [name] will compare recordings of both group exercise and support sessions with a check list of exercises/topics scheduled to be included in each session. Health educators covering <80% of scheduled content, or failing to deliver physical activity as prescribed, will receive additional training from [name], and will be dismissed if the problem recurs.

ASSESSMENTS

MPA. Primary outcome (Baseline (0 mos.)- 6 mos.)/Secondary outcomes (0-18 mos.)

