Schedule. MPA in adults with AD and their caregiver will be assessed at baseline (1 wk. prior to starting the intervention), 3, 6, 12, and 18 mos. Equipment. MPA/sedentary time will be assessed using an ActiGraph model wGT3x-BT tri-axial accelerometer (3.3 x 4.6 x 3.5 cm, wt. = 19 g., dynamic range \pm 8 g). The ActiGraph provides valid and reliable assessments of MPA/sedentary time in adults (70-73). Our group has used the ActiGraph in several trials in a variety of populations including adolescents (74) and adults with IDD (75), and in typically developing children (76, 77) and adults (78, 79). Protocol. There is a lack of consensus on the best protocols to collect, process, and score ActiGraph data (80-82). Thus, our decisions regarding ActiGraph location, monitoring period, data processing etc. were based on current practice, as described below. Participants will be asked to wear the ActiGraph on a belt over the non-dominant hip at the anterior axillary line during waking hours for 7 consecutive days, except for bathing and swimming. A 7-day monitoring period provides a reliable estimate of MPA (81, 83-85). The hip, rather than the wrist location, will be used due to the lack of comparable data and established protocols for assessment of MPA using wrist-worn ActiGraphs (86-88). ActiGraph distribution/reminders. Research staff will distribute and

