Statistical design. Baseline equivalence. The distributional properties of baseline demographic characteristics (MPA, BMI, age, sex, race/ethnicity, etc.) and dyadic relationship between adults with AD and their caregiver (quality, type, number of caregivers) will be inspected within the sample and between the RGV and EUC arms. Variables that demonstrate a significant nonequivalence between RGV and EUC arms will be statistically controlled in the hypothesis testing to improve accuracy of our inferences on intervention effects. Additionally, variables that significantly differ between dyads that dropped out and those that did not will be controlled to minimize any systematic bias stemming from attrition.

Primary aim: *To compare MPA (min/wk.) across the 6-mo. active intervention in adults with AD randomized to RGV and EUC.* Our analysis will account for/evaluate the clustering of observations (repeated measurements; level 1) within participants (level 2) and dyads (level 3; if multiple caregivers) by estimating intra-class correlations and variances/covariances of regression

coefficients at, and across, different levels in random-effects multilevel models (mixed models). To address the aim, models will examine overall between-arm difference in MPV across time (group effect), linear/non-linear change in MPV over time (time effect), and, if appropriate, between-arm difference in this change (group-by-time interaction), while controlling for (i) the number of contacts with research staff and (ii) the baseline characteristics imbalances between participant subgroups (RGV vs. EUC, dropouts vs. completers). For example, a significant interaction would indicate that adults with AD in the RGV arm achieve more minutes of MPA compared to those in the EUC arm and this difference becomes greater as intervention participation increases, i.e., in the later mos.

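### The primary model picks baseline covariates by significance test, so adjustment for baseline MPA and sex is not guaranteed, and it names neither the deciding term nor the role of baseline MPA

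*Combined protocol and SAP*

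**What the plan says.** All references are to the combined protocol and SAP.

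- **Covariates (section V.A, Baseline equivalence).** MPA, BMI, age, sex and other characteristics are to be inspected. Then "Variables that demonstrate a significant nonequivalence between RGV and EUC arms will be statistically controlled in the hypothesis testing", and "variables that significantly differ between dyads that dropped out and those that did not will be controlled".
- **Primary model (section V.A, Primary aim).** The mixed model is fitted "while controlling for (i) the number of contacts with research staff and (ii) the baseline characteristics imbalances between participant subgroups". The number of contacts is therefore the only covariate fixed in advance.
- **Terms.** The "models will examine overall between-arm difference in MPV across time (group effect"), a time effect and, "if appropriate, between-arm difference in this change (group-by-time interaction"). (The text writes MPV; I read it as MPA.) No term is named as deciding. The group effect is listed first, but the only worked example of a positive finding is a significant interaction.
- **Aim and window.** The opening statement of the aim is "To compare total MPA (min/wk.) across the 6-mo. active intervention in adults with AD and their caregiver". The restatement in V.A and the power statement name adults with AD only. The Assessments heading reads "MPA. Primary outcome (Baseline (0 mos.)- 6 mos.)/Secondary outcomes (0-18 mos"), and MPA "will be assessed at baseline (1 wk. prior to starting the intervention), 3, 6, 12, and 18 mos".
- **Power (section C).** At least 80% to detect 10 min/d (SD 30) with 42 or more per arm, using 21 MPA measurements and a correlation of 0.22 between repeated measures.
- **Randomisation (section E).** Cohorts of about 20 dyads, stratified by sex, 1:1.

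**The concern.** Testing randomised arms for baseline differences is a poor way to choose covariates. A covariate earns its place by predicting the outcome, and baseline MPA should predict later MPA whether or not the arms happen to differ. Under the arm screen it enters in about 5% of trials. Sex, being stratified, will hardly ever be selected: illustrative splits of 22/50 against 20/50, or 25/50 against 20/50, give p = 0.69 and 0.31.

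The role of the baseline week is a separate gap with two exclusive readings.

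- **Reading A: baseline is not a response.** This fits an aim about the intervention period, since baseline is measured before it starts. Baseline MPA then enters only if a screen selects it.
- **Reading B: baseline is a response.** This fits the Assessments heading and, by inference, the 21 measurements, which equal 3 weeks of 7 days only if the baseline week is counted. Baseline MPA is then in the model, but a group effect averaged over months 0, 3 and 6 includes a week in which no difference is expected.

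At stake are precision under A and, under B, what the primary test estimates.

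**Working it through.** **Inputs.** From section C: 42 per arm, 10 min/d, SD 30 per day, correlation 0.22. From Assessments: 7-day weeks at 0, 3 and 6 months. Assumed: two-sided alpha 0.05 (not stated), no difference at baseline, 10 min/d at both months 3 and 6, no lost weeks, no contacts term. Power is from the noncentral t with 2n−2 df (2n−3 with a covariate); SE = 30 × √(2 × var/n).

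**1. The plan's figure.** For 21 days with equal correlation 0.22 and 10 min/d throughout, var = (1 + 20 × 0.22)/21 = 0.2571, SE = 3.32, power 0.845. The stated 80% is reproduced, but with the full difference credited to the baseline week.

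**2. 0.22 as a between-day correlation.** Week-mean variance v = (1 + 6 × 0.22)/7 = 0.3314 (units of 30²). Between-week correlation r = 0.22/0.3314 = 0.664.

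| Contrast | Variance | Effect | SE | Power |
|---|---|---|---|---|
| A: months 3 and 6, unadjusted | v(1+r)/2 = 0.2757 | 10 | 3.44 | 0.82 |
| A: same, always adjusted for baseline MPA | v((1+r)/2 − r²) = 0.1297 | 10 | 2.36 | 0.99 |
| B: group effect over 0, 3, 6 | v(1+2r)/3 = 0.2571 | 20/3 = 6.67 | 3.32 | 0.51 |
| B: post minus baseline | 1.5v(1−r) = 0.1671 | 10 | 2.68 | 0.96 |

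Adjustment leaves 0.1297/0.2757 = 0.470 of the variance, a 53% reduction. At 40 per arm (50 less 20%) the four powers are 0.80, 0.98, 0.49 and 0.95.

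**3. The screening rule under reading A, simulated.** With the arm screen, baseline MPA is selected in about 5% of trials, power is about 0.84 and type I error about 0.035. With both screens, if baseline MPA is unrelated to dropout, selection is about 10%, power about 0.85 and type I error about 0.036.

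**4. 0.22 as a between-week correlation.** Now r = 0.22 and v = (1 + 6w)/7, where w is a within-week correlation that the documents do not give. The variance reduction from adjustment is r²/((1+r)/2) = 0.0484/0.61 = 8% for every w.

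| Assumed w | A unadjusted | A adjusted | B group effect | B post minus baseline |
|---|---|---|---|---|
| 0.3 | 0.86 | 0.89 | 0.63 | 0.60 |
| 0.4 | 0.79 | 0.82 | 0.55 | 0.52 |
| 0.5 | 0.73 | 0.76 | 0.49 | 0.46 |
| 0.6 | 0.66 | 0.70 | 0.43 | 0.41 |

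**The case against.** The strongest reply has four parts.

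**None of these powers is for the model in V.A.** That model always contains the number of staff contacts, which in the RGV arm may include the group sessions and so be closely tied to arm. This stands. The figures compare simplified models, and the contacts term needs its own resolution.

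**Unadjusted reading A meets the stated 80% at between-day 0.22, and the gain may be small.** This also stands. The loss is against a better analysis of data already collected, and it runs from 53% of the variance down to 8%. The documents do not support a firm promise of 0.99.

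**The evidence favours baseline as a response, and the interaction example rescues the test.** The heading and the 21 measurements do lean that way, but listing MPA among the screened variables points the other way. The post-minus-baseline contrast, which V.A does not name, has 0.96 only at between-day 0.22; at between-week 0.22 it has 0.60 to 0.41.

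**The screens are a stated rule based on baseline and dropout data, and analysts are blinded.** Correct. It would be too strong to say that covariates are chosen freely after seeing results. Selection may also exceed 10%: with 16 of 100 dropping out and an assumed 0.5 SD difference in baseline MPA, the dropout screen alone would select it in about 44% of trials. Neither point names the deciding term or settles the role of baseline.

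A reader might also infer that a significant result on either term counts as success, with inflated type I error. The documents use either-term wording only for the exploratory step in V.A, not for the primary aim, and the screening itself is slightly conservative.

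**Conclusion.** The concern holds as a specification and precision problem that should be fixed; it is not an error-rate problem. V.A guarantees adjustment for neither baseline MPA nor the sex stratum, names no deciding term, and leaves the role of baseline MPA open.

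Under the listed assumptions the cost in reading A is the gap between about 0.84 and 0.99 if 0.22 is between days, or 3 to 4 points if it is between weeks. In reading B with the group effect deciding, power is about 0.51 (0.63 to 0.43 at between-week 0.22), below the stated 80%. The missing specification does not depend on what 0.22 means; its size does. The gain from adjusting for sex cannot be computed from the documents.

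**What to change.** - Name one primary contrast in adults with AD: the RGV−EUC difference in MPA averaged over months 3 and 6, with group-by-time secondary.
- Always adjust for baseline MPA, either as a covariate or through a longitudinal model with a common baseline mean, and for sex as used in the randomisation.
- Replace both screens with a covariate list fixed in advance that includes expected predictors of dropout. This keeps the plan's guard against attrition bias. The Missing data paragraph handles dropout by FIML and mentions auxiliary variables only for imputing nonresponse.
- Restate primary power for that adjusted contrast, giving alpha and saying whether 0.22 is between days or between weeks.
- Settle the contacts term separately.

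The cost is SAP wording, one advance decision on dropout predictors and a few degrees of freedom. No new data are needed.

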
Potential for video conferencing. An intervention delivered via video conferencing to adults with AD and their caregivers in their homes, represents a potentially effective approach for increasing MPA in this group. This approach requires no travel, since the need for transportation to a medical clinic or other community facility is eliminated, and offers the potential for peer support and socialization, which may be important for initiation and maintenance of MPA. To assess the feasibility of the video conferencing approach, we recently completed a 12-wk. single arm pilot trial in 9 adults with AD (age = 74 ± 16 yrs., 56% female) and their family caregiver (dyads) (age = 67 ± 13 yrs., 67% female) funded by the University of Kansas Alzheimer's Disease Center (KU-ADC). Three, 30-min. group exercise sessions/wk. were delivered by trained health coaches via video conferencing (Zoom® software) on a tablet computer (iPad®) to 4-6 dyads in their homes. Each session included a warm-up (5 min), aerobic (10-15 mins) and resistance exercise (5-10 mins), and cool down (5 min). Participants wore a Fitbit activity tracker over the 12 wk. intervention to assess

the duration and intensity of the physical activity sessions and total weekly MPA (min./wk.). Participants received brief monthly phone calls (<5 min) from the health coach to provide strategies for encouraging and supporting MPA, and as a reminder of the upcoming video session. Session attendance was ~77% for adults with AD and ~79% for caregivers. MPA per group session averaged 20.4 ± 8.5 (at ~ 57% of estimated HR_{max}) and 27.0 ± 8.2 min/session (at ~61% of estimated HR_{max}) in adults with AD, and their caregiver, respectively. Attendance at the monthly individual support session was 87% for both the adults with AD and the caregivers. At baseline, total weekly MPA was 53.9 ± 34.5 min/wk. in adults with AD and 166.4 ± 54.7 min/wk. in caregivers, and increased by 24 min/wk (45%) and 49 min./wk. (30%), in adults with AD and caregivers, respectively. Compliance with the Fitbit protocol was acceptable as adults with AD and caregivers wore the Fitbit on $82.5 \pm 27.7\%$ and $79.9 \pm 25.7\%$ of the total study days, respectively. Exit surveys indicated that participants generally enjoyed the program, preferred a home-based program vs. traveling to an exercise facility, preferred group over individual exercise sessions, and were interested in participating in longer sessions.

C. Rationale

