We will study older adults (age ≥ 55 yrs.) with mild to moderate AD (n=100) and their caregiver (n=100) randomized (1:1) to one of two intervention delivery strategies for increasing MPA; real-time group video conferencing (RGV) vs. enhanced usual care (EUC). All participants will be provided with an iPad® for intervention delivery, Fitbit for self-monitoring MPA, and will be asked to complete 150 min of MPA/wk. Dyads in the RGV arm will be asked to complete three 45 min sessions that include aerobic, resistance, and balance/coordination exercises delivered by a trained

health coach via Zoom® software on an iPad® during mos. 0-6, and 1 session/wk. during mos. 7-12 to groups of 5-8 dyads in their home. Dyads in the EUC arm, will be given an exercise plan to do own their own. Dyads in both arms will be provided with written materials regarding exercise and physical activity from the National Institute on Aging and will be asked to complete brief (15-20 min) FaceTime™ meetings (0-6 mos.= 2/mo.; 7-12 mos.= 1/mo.) with the health coach to discuss progress, provide support and receive additional guidance on how to increase MPA. Our primary outcome, MPA, will be assessed by accelerometer across the 6 mo. active intervention and total 18 mo. study (secondary outcome).

C. Sample size, statistical methods, and power calculation

We will recruit 100 adults with AD and their caregiver (100 dyads) at baseline to achieve adequate power to test both short-term (0-6 mos.) and long-term (0-18 mos.) effects of the intervention. Our power calculation, based on 21 measurements of MPA, 35 measurements of secondary and exploratory outcomes, a previously observed correlation of 0.22 between repeated measures, and a high attrition rate of ~20%, indicated that this sample size (≥ 42 /arm after attrition) would produce $\geq 80\%$ power to detect an anticipated difference of 10-min/d in MPA ($SD=30$ min/d; $f=0.17$) between adults with AD randomized to RGV and EUC during the active intervention (0-6 mos.). This sample size would also yield $\geq 81\%$ power to test a between-arm difference as small as $f=0.15$, e.g., 6 ± 30 min/d in MPA, during maintenance (7-12 mos.) and no contact (13-18 mos.).

D. Subject Criteria (See Vulnerable Populations appendix, if applicable):

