Primary care physician (PCP) clearance will be required of participants with AD and their caregiver. To enhance generalizability, individuals taking AD or other medications, or receiving treatment for other chronic diseases, or with risk factors such as hypertension, tobacco use, lipid abnormalities, T2DM, etc., will be allowed to participate with PCP clearance. *Inclusion criteria (Adults with AD):* *Inclusion:* 1) Very mild to moderate dementia (MMSE or STMS ≥ 11 ; Telephone Interview for Cognitive Status (TICS) ≥ 6). 2) Age ≥ 55 yrs. 3) Low-risk of falls, assessed by PCP consent 4) Ability to participate in MPA, e.g., walk including with an assistive device, as verified PCP clearance. 5) Ability to communicate verbally. 6) Vision and hearing sufficient to safely comply with the intervention program as verified by PCP clearance. 7) Reside at home and receive support from a caregiver. 8) Internet access in the home. *Exclusion criteria (Adults with AD):* 1) Current exercise, i.e., > 3 , 30-min bouts of planned exercise/wk. 2) Clinically significant psychiatric disorder; systemic illness or infection likely to affect safety; clinically-evident stroke; myocardial infarction or coronary artery disease in the last 2 yrs.; cancer in the last 5 yrs.; or significant pain or musculoskeletal symptoms that would prohibit exercise. 4) Unwilling to be randomized. *Inclusion criteria (caregivers):* 1) Age ≥ 18 yrs. 2) Spends at least 20 hrs./wk. with the adult with AD. *Exclusion criteria (Caregiver):* 1) Unable to participate in MPA, i.e., brisk walking. 2) Unwilling to be randomized. 3) Serious medical risk, such as cancer within the last 5 yrs. or cardiac event, i.e., heart attack, stroke, angioplasty within the last 2 yrs.

E. Specific methods and techniques used throughout the study

Randomization. Cohorts of ~20 dyads will be stratified by sex and computer randomized by the study statistician with equal allocation to the RGV or EUC arms. Intervention assignments will be concealed in envelopes and delivered to the study coordinator. Assignments will be revealed to adult/caregiver dyads at the orientation session described below.

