
RGV arm

Schedule. Group exercise sessions will be scheduled on 3 non-consecutive days/wk.(M,W,F) during the active intervention (0 to 6 mos.) and 1 day/wk. during maintenance (mos. 7-12). Group sessions will not be scheduled during the no-contact period (13-18 mos.). During orientation sessions, dyads will be asked to provide times of the day, between 10 a.m. and 7 p.m., that would be most convenient to complete the group sessions. Based on this information we will offer dyads in each cohort the choice between 2 potential session times each day. Prompts reminding adults with AD/caregivers of upcoming sessions will be sent using iMessage on the iPad® (adult with AD)/iPod® (caregiver) and iCalendar. Session delivery. Real-time exercise sessions will be delivered to adults with AD/caregiver dyads in their home by a trained health coach experienced in working with adults with AD using Zoom® video conferencing software. This software allows multiple users to see and interact with each other and the health coach via the iPad®. The health coach will conduct exercise sessions from our remote-delivery exercise studio (see facilities) which we used for remote delivery of exercise in our AD pilot (61) and in trials with adolescents with intellectual and developmental disabilities (IDD) (62), and adults with Down Syndrome (63). Tutorials describing trouble shooting for common technical problems with the Zoom® software, e.g., internet connectivity etc., will be loaded on the iPad®. Dyads with technical issues during the intervention may also contact research staff by phone or email. An alternative caregiver (other family member, staff etc.) may participate in the event that the caregiver enrolled in the trial is unable to attend an exercise session. These procedures were used in our AD pilot trial where alternative caregivers attended 8% of sessions (61). MPA session content. [name], a physical therapist, will develop the exercise program for this trial. He developed the exercise content for our pilot trial in adults with AD and has been involved in other exercise trials for adults with AD (R01AG034614, R01AG033673) (64-66). Each session will include a warm-up (~5 min), moderate intensity aerobic activity (3-5 METs) (~30 min), resistance and balance/coordination exercise (~5 min.), and cool-down/stretching (~5 min.). The MPA portion will ramp from 10 min/session at wk. 1 to the goal of 30 min/session at wk. 8. Each session will include aerobic activity, e.g., walking/jogging standing in place or sitting in a chair, sit to stand, dance movements; resistance exercise, e.g., TheraBand®-arm curls, leg extensions, side leg raises, and seated rows; and balance exercise, e.g. heel to toe walks, balance walk, and standing on one foot with/without support of a chair). [name] will provide modifications for participants having difficulty with any specific exercises. Health coaches will encourage interactions between participants during group sessions and ensure interactions between participants do not focus on dementia (67), but rather on issues relative to supporting their peer's efforts to increase MPA. Additionally, the Zoom app used for the sessions allows for messaging between participants during and after the group exercise sessions. Caregivers will be allowed to message the research staff and other caregivers for help and support both during the sessions and outside of the group sessions. We will keep copies of the messages sent to research staff on the KUMC P-Drive. Outside session MPA. Group exercise sessions will provide the potential to accumulate 90 min/wk. (3 sessions x 30 min/session) during the active intervention (0-6 mos.) and 30 min/wk. (1 session) during maintenance (7-12 mos.). Thus, MPA in addition to that accumulated in group sessions will be required to meet the MPA goal of 150 min/wk. To provide a transition from a sedentary to a more physically active lifestyle we will recommend goal of 45 min of MPA/wk. at wk. 1 and increase the goal by 15 min/wk.to reach the 150 min/wk. goal at wk. 8. We successfully used this MPA progression in previous trials in adults with AD (57). At the completion of each group session health coaches will provide a "weekly challenge" for participants to try a new activity or create and perform a new exercise routine etc. in order to reach the 150 min./wk. goal. Additionally, the NIA pamphlet "Exercise and Physical Activity: Your Everyday Guide" will be loaded on the iPad to assist participants in meeting the 150 min./wk. goal. Video recordings. Video recordings of all group exercise sessions will be uploaded to Dropbox®. Participants/caregivers will be encouraged to access video recordings using their iPads®/iPods® to assist with meeting the 150 min./wk. goal. Frequency and duration of participant/caregiver video access will be tracked using Dropbox® analytics. No contact follow up (13-18 mos.). Group video and individual support sessions will be discontinued. Participants will be

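### RGV is delivered live in groups of 5-8 dyads and EUC individually, but the primary and secondary models have no exercise-group level; the likely type I error inflation is modest.

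*Combined protocol and SAP*

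**What the plan says.** Under Statistical and Data Analysis, the primary aim describes random-effects multilevel models and names the levels: "Our analysis will account for/evaluate the clustering of observations (repeated measurements; level 1) within participants (level 2) and dyads (level 3; if multiple caregivers"). The secondary aim fits models of the same kind to the other outcomes. Neither mentions the exercise group.

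Study Type and Design delivers RGV sessions "to groups of 5-8 dyads in their home", while EUC dyads receive a plan to follow by themselves. Randomization states that "Cohorts of ~20 dyads will be stratified by sex and computer randomized by the study statistician with equal allocation". In the RGV arm's Schedule, "During orientation sessions, dyads will be asked to provide times of the day" that suit them, and then "we will offer dyads in each cohort the choice between 2 potential session times each day". Under session content, "Health coaches will encourage interactions between participants during group sessions". The background section on video conferencing says the approach "offers the potential for peer support and socialization, which may be important for initiation and maintenance of MPA".

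The only correlation named in the power calculation is "a previously observed correlation of 0.22 between repeated measures".

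**The concern.** The design is partially nested: RGV dyads share a coach, a time slot and peers several times a week for six months, and EUC dyads share no exercise group. Individual randomisation does not remove correlation that arises afterwards within a group. The plan itself names peer support as a reason RGV may work, so positive correlation among group-mates is plausible, though not demonstrated.

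A model that treats RGV dyads as independent then understates the variance of the RGV mean. The primary test would reject too often under the null and its confidence interval would be too narrow. The secondary models inherit the same problem. The plan also does not say how a dyad's group is defined or recorded. Attendance is described only as a percentage of possible sessions, so group membership might not be recoverable later.

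**Working it through.** **Inputs from the documents.** 100 dyads, 1:1; at least 42 per arm after attrition; difference 10 min/d, SD 30; 21 measurements; repeated-measures correlation 0.22; cohorts of about 20 dyads; two session times per cohort; groups of 5-8.

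**Assumptions.** Two-sided alpha 0.05 and group ICC 0.02, 0.05 or 0.10 on the person mean. The documents state neither. The calculation is an unadjusted comparison of person means.

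**The plan's own power.** The SD of a person mean is 30 × sqrt((1 + 20 × 0.22)/21) = 15.21. The SE of the difference is 15.21 × sqrt(2/42) = 3.320, so 10/3.320 = 3.012. Power is Φ(3.012 − 1.96) = 85.4%, consistent with the stated figure of at least 80%.

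**Number of groups.** 100/20 = 5 cohorts. Each has about 10 RGV dyads over two times, or 5 per group, giving about 10 groups. Analysed dyads per group: m = 42/10 = 4.2.

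**Inflation.** The RGV design effect is DE = 1 + (m − 1) × ICC; for EUC it is 1. The true SE exceeds the planned SE by r = sqrt((DE + 1)/2). Type I error = 2(1 − Φ(1.96/r)). Normal-approximation power with the correct SE = Φ(3.012/r − 1.96).

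| ICC | DE | r | Type I error | Power |
|---|---|---|---|---|
| 0 | 1.000 | 1.000 | 5.0% | 85.4% |
| 0.02 | 1.064 | 1.016 | 5.4% | 84.3% |
| 0.05 | 1.160 | 1.039 | 5.9% | 82.6% |
| 0.10 | 1.320 | 1.077 | 6.9% | 79.9% |

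**Allowing for the baseline week.** The MPA schedule measures 7 days at baseline, 3 and 6 months, and 3 × 7 = 21. Baseline precedes the intervention, so no group effect can exist then. If the tested mean includes that week, and with compound symmetry at 0.22, the ICC is multiplied by (2/3)² × (0.22 + 0.78/14)/(0.22 + 0.78/21) = 0.477. The three ICCs then act as 0.010, 0.024 and 0.048, and type I error is 5.2, 5.4 and 5.9%.

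**Larger groups.** With 8 analysed dyads per group and ICC 0.10, DE = 1.70, r = 1.162 and type I error is 9.2%. With the baseline dilution, DE = 1.334, r = 1.080 and it is 7.0%. Such groups can arise if dyads choose the two times unevenly, or if all 8 RGV dyads in a cohort of 16 choose one time.

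**Power with small-sample degrees of freedom.** Using 9 df for 10 RGV groups and 41 for EUC, Satterthwaite df are 29.5 at ICC 0, then 28, 27 and 25. Noncentral-t power is 83.0%, then 81.7, 79.8 and 76.6%.

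**Simulation of a group-effect model** (person means, no cohort or baseline term, 100,000 runs per setting), at ICC 0 / 0.02 / 0.05 / 0.10:

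- type I error 4.1 / 4.2 / 4.4 / 4.6%;
- power 81.4 / 80.4 / 78.6 / 75.7%;
- group variance estimated as zero in 54 / 48 / 40 / 28% of runs.

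Without the group term, type I error on the same data was 5.1 / 5.4 / 5.9 / 6.8%.

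**The case against.** The strongest reply is that the effect is small and the remedy imperfect. Several parts of it stand.

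- The measurement schedule makes the diluted range, 5.2-5.9%, at least as faithful to the plan as 5.4-6.9%.
- The ICC and alpha are assumptions. Peer support could raise the whole arm's mean without making groups differ, and a common programme with content checks would limit such differences.
- Dyads choose their slot after randomisation. Similarity due only to who picks which slot does not invalidate the planned SE, yet a group effect treats it as clustering. In a null simulation of such sorting, the grouped test rejected 3.1%.
- Cohort effects reach both arms and cancel in the comparison. An RGV-only group effect without a cohort term absorbs them. At a cohort ICC of 0.05 the grouped test rejected 3.8%, against 5.0% with cohort adjusted.
- The planned model also adjusts for staff contacts and tests group-by-time, which these calculations do not reproduce.

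These points limit the size of the problem and shape the fix, but they do not supply the missing level. The promise under the exploratory aim to design models carefully concerns process variables, not the primary test.

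A reader might infer that the stated power is wrong or that the primary test is seriously invalid. The documents support neither: they give no group ICC, and the stated power reproduces when groups are ignored. Nor should 9% be read as the expected error, since it needs both the largest groups and the top of the assumed ICC range.

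**Conclusion.** The omission is real and affects the primary and the similar secondary models. Its direction is anti-conservative if the group itself induces positive correlation. For about 10 groups of 4.2 analysed dyads, two-sided 5% and ICC 0.02-0.10, type I error is about 5.2-5.9% with a group-free baseline week in the tested mean and 5.4-6.9% without that dilution. Groups of 8 would give up to about 7-9%. The claim of at least 80% power is not refuted, but it rests on a negligible group ICC that the plan neither states nor justifies. This is worth correcting before the data are analysed; it is not a fatal flaw.

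**What to change.** In the primary and similar secondary models:

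- add randomisation cohort as a fixed effect;
- adjust for baseline MPA, or for the baseline value of the outcome;
- add a random effect for exercise group in the RGV arm only, with each EUC dyad its own cluster;
- use Kenward-Roger or Satterthwaite degrees of freedom.

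Define the group by cohort and the session time first selected, and record it for every RGV dyad whatever its later attendance. Report the model without the group term as a sensitivity analysis, and report primary power over group ICC 0-0.10.

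Do not cluster the RGV arm by cohort instead, even if dyads switch times. That leaves about 5 clusters and, by the same noncentral-t method, power of about 80 / 77 / 71 / 64% at ICC 0 / 0.02 / 0.05 / 0.10.

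The cost is SAP wording and one recorded field per RGV dyad, with slightly wider intervals. Power is about 83% at ICC 0 and 82 / 80 / 77% at 0.02 / 0.05 / 0.10 before cohort adjustment, which lowers the degrees of freedom further. The group variance will often be estimated as zero. Some conservatism remains if groups differ only through choice of slot, which baseline adjustment only partly removes.
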